### **C. Study Design and Research Methods.**

Timeline

Activity	Year			
	1	2	3	4
Study start-up	x			
Patient recruitment		x	x	x
Outcomes measurement, implementation data collection		x	x	x
Analysis and write-up				x

The proposed study will be completed within a 4 year timeline (**Table 2**). Collection and analysis of medical record information will continue for up to ten years after a patient's active study participation concludes.

The table illustrates timing for completion of the main study tasks using 6-month increments. We will try to complete recruitment over a 19 month period, but have budgeted for completing recruitment over 25 months.

### Recruitment Targets and Tracking

#### **Aim 1:**

The estimated flow of patients and overall accrual goals are displayed in **Figure 2**. We will aim to randomize 8 patients per month at each site (16 total) over a 19 month period. This will yield one intervention patient per week per site on average. If enrollment is slower than anticipated, we will still be able to complete the study on time if 6 Veterans per month are randomized at each site over a 25 month period.

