### Study population:

**Aim 1:** A total of 400 adult subjects will be randomized in a 1:1 ratio to one of 2 treatment arms: 1) enhanced usual care or 2) team-based palliative care intervention plus usual care. A component of the study intervention involves speaking to study subjects' informal (family) caregivers. The eligibility criteria (**Table 1**) aim to enroll Veterans with a diagnosis of CHF, ILD, or COPD who are at risk of hospitalizations or death, have poor quality of life, and are able to participate in the intervention.

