#### **Aim 2a:**

**Patient interviews:** We anticipate at most 120 eligible patients of the 200 receiving the intervention will participate, as they have already participated in the intervention and would be likely to offer feedback.

**Intervention personnel:** We expect all intervention team members to participate as they are invested in the intervention and would be likely to want to provide feedback.

[figure not shown]
**Primary care providers whose patients have received the intervention:** We expect approximately 100 providers will participate.

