#### Sample Size

The sample size was planned to detect a clinically significant change on the primary outcome, quality of life. We plan to enroll 400 Veterans and anticipate 5% will die and 15-20% will have missing outcome data because they did not complete surveys or dropped out. Thus approximately 115 Veterans per arm will complete the study. With this sample size, we will have 85% power to detect a moderate effect size of 0.4 (two-sided test, alpha=0.05). The minimal clinically important difference on the FACT-G is 4-6 points, and with a standard deviation of 15, a Cohen's d effect size of 0.4 will be on the high end of clinical significance. We believe this is appropriate as this is a personnel-intensive intervention. **Table 3** illustrates a range of sample sizes per study arm with different power and effect size assumptions.

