**Table 6. Intervention implementation (Aim 2a) objectives, data collection, and analytic frameworks**

Objective	Data Source	Sample Size	Analytic Framework
Assess intervention component implementation	Intervention database	150	Quantitative : descriptive statistics by site and illness of the variability in "dose" and content of the delivered intervention
Identify critical intervention components and processes and facilitators/barriers to intervention implementation	Brief patient interviews	100	Qualitative analysis of data using the following CFIR* Domains, Constructs , allowing for emergence of new codes/ideas
	Intervention close out summary	150	Intervention Characteristics Relative advantage, complexity, cost, design quality and packaging
	Focused group discussion with intervention team	1-2	Characteristics of Individuals Knowledge & beliefs about Intervention
	Survey of PCPs whose patients have received the intervention	150	Outer Setting Patients' Needs and Resources Inner Setting Implementation climate, relative priority, readiness for implementation

\*CFIR, Consolidated Framework for Implementation Research

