### Study Procedures for Positive Depression Screening:

The outcome measures administered to all subjects include a screen for depression (a score of greater than 10 on the PHQ-8). Because the intervention focuses on depression, these issues will be addressed in intervention subjects as part of the intervention. Subjects in the *usual care* group who score above the screening cutoff for moderate depression will be advised of this and given resources for depression care, including advice to discuss these results with a health care professional. In addition, the results will be forwarded to their health care professional.

**Aim 2a:** To understand why particular intervention components and processes were most critical from the perspectives of patients, intervention team members, and PCPs, we used the Consolidated Framework for Implementation Research (CFIR) to guide data collection (**Table 6**). CFIR, which is well-established in VA, was chosen as it provides a useful framework for considering contextual facilitators and barriers to intervention implementation. Specific domains and constructs from CFIR were chosen to reflect the areas that were important to patients, intervention team members, and providers in the CASA pilot study. The following data sources will be used for Aim 2a:

*Intervention database:* The following data will be collected: (1) team meeting duration, number of patients discussed and time spent per patient, medical orders (e.g., tests, medications) written and completed; (2) nurse and social worker visit duration, number, and content (using a brief checklist) for each patient.

*Brief patient interviews:* After the outcome measurement at 6 months, we will conduct brief in-person or telephone interviews with Veterans randomized to the intervention arm. Interviews will be conducted to elicit patient views about different parts of the intervention (e.g., nurse vs. social worker); how to improve the content and value of the intervention; communication and coordination; and to what extent they continue to sustain their use of the intervention after the study. We will continue to interview as staff time permits or until no new information emerges from continuing interviews, a principle known in qualitative research as “saturation.” We will interview a subset of patients completing the intervention every 6 months in order to account for potential

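### The stated 400 randomized does not agree with the accrual plans (304 and 300) or with 115 completers per arm at 85% power, all of which fit a trial of about 300

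*Protocol*

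**What the plan says.** Three places in the protocol support a total of 400:

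- Study population (section IV.B): "A total of 400 adult subjects will be randomized in a 1:1 ratio".
- Sample Size (section IV.C): "We plan to enroll 400 Veterans and anticipate 5% will die and 15-20% will have missing outcome data".
- Recruitment Targets and Tracking, Aim 2a: "We anticipate at most 120 eligible patients of the 200 receiving the intervention will participate".

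Other figures do not follow from 400:

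- Recruitment Targets and Tracking, Aim 1, main plan: "We will aim to randomize 8 patients per month at each site (16 total) over a 19 month period".
- The same section, fallback for slow enrolment: the study will still "be able to complete the study on time if 6 Veterans per month are randomized at each site over a 25 month period".
- Sample Size, straight after the loss assumptions: "Thus approximately 115 Veterans per arm will complete the study". This is paired with 85% power for an effect size of 0.4 (two-sided, alpha 0.05, SD 15). Table 3 gives 114 per arm for that cell.

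The Timeline text says 19 months is the recruitment aim and 25 months is what has been budgeted. Table 6 gives 150 for the intervention database (objective: "Assess intervention component implementation"), a source described under Aim 2a in section IV.D as holding "nurse and social worker visit duration, number, and content (using a brief checklist) for each patient". The SAP gives no sample size.

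**The concern.** The total, the monthly pace, the recruitment period, the expected completers and the power should all describe one trial, and here they do not. The Sample Size section presents 115 completers per arm as the consequence of enrolling 400 and losing 20–25%, but that step does not work. Separately, both accrual plans stop about 100 patients short of 400.

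What is at stake is the definition of completed enrolment. If recruitment stops near 300, the trial delivers the completers and power it promised, yet on paper it looks 25% short of its stated size. If it goes on to 400, the statement that the slower pace finishes on time is false, and the stated completers and power are too low. Anyone monitoring accrual against this protocol, or judging later whether the trial reached its target, has two incompatible yardsticks.

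**Working it through.** **Inputs (all from the protocol).** Total 400, allocation 1:1; loss 5% deaths plus 15–20% missing, so 20–25%; 115 completers per arm; effect size d = 0.4, SD 15, two-sided alpha 0.05, power 85%; accrual 8 per site per month for 19 months or 6 per site per month for 25 months, two sites; recruitment budgeted for 25 months.

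**1. The power step reproduces.** A two-sample t-test with 115 per arm and d = 0.4 has 85.6% power (85.8% by the normal approximation), against 85% stated. Solving for n at 85% power gives 113.2, which rounds up to Table 3's 114. The power calculation itself is sound.

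**2. The step from 400 to 115 does not.** Completers per arm = N/2 × (1 − loss).

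| N | 25% loss | 20% loss | Power at d = 0.4 (t-test) |
|---|---|---|---|
| 300 | 112.5 | 120 | 84.8–87.0% |
| 304 | 114 | 121.6 | 85.2–87.4% |
| 400 | 150 | 160 | 93.2–94.6% |

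Applying the losses in sequence (0.95 × 0.80 to 0.95 × 0.85) changes little: 114–121 per arm from 300, and 152–161.5 from 400.

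**3. Working backwards from 115 per arm (230 in all).**
- Loss implied from 400: 1 − 230/400 = 42.5%.
- Loss implied from 300: 1 − 230/300 = 23.3%, within the stated 20–25%.
- Enrolment implied by the stated loss: 230/0.80 = 287.5 to 230/0.75 = 306.7, so 288–307.

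**4. Accrual.**
- Main plan: 8 × 2 × 19 = 304, which is 96 (24%) short of 400.
- Fallback: 6 × 2 × 25 = 300, which is 100 (25%) short.
- Time to 400 at 12 per month: 400/12 = 33.3 months, 8.3 beyond the 25 budgeted.
- Time to 400 at 16 per month: 400/16 = 25 months, the whole budgeted period.
- Pace needed for 400 in 19 months: 400/(2 × 19) = 10.5 per site per month.

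**5. Detectable difference at 85% power (SD 15).** 115 per arm: d = 0.397, or 5.95 FACT-G points. 150 per arm: d = 0.347, or 5.21. 160 per arm: d = 0.336, or 5.04.

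**6. Table 6.** The 150 for the intervention database is half of 300, but it is also 75% of 200, so it does not settle which total was meant.

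**The case against.** The strongest reply is that the protocol states only one total. 400 appears twice, and the 200 intervention patients agree with it; 300 is never written and has to be inferred. That is right, and the accurate statement is that the accrual and completer figures do not follow from 400. It does not remove the conflict.

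Other points on that side:

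- **Enrolled versus randomized.** One might read 400 as enrolled and 300 as randomized. The Study population section says 400 are randomized, and the accrual plans also count randomized patients, so this fails.
- **Figure 2.** The accrual goals are said to be shown there, and the figure is not available. It might show which total was intended, but it could not make both sets of text true.
- **Feasibility.** The faster pace kept up over the budgeted 25 months reaches exactly 400, and section E lists remedies for slow recruitment. This stands: only the 19-month plan and the 12-per-month fallback conflict with 400.
- **Table 6.** It also gives 150 for the primary care provider survey, against about 100 expected in the recruitment text, and 100 patient interviews against at most 120. Its counts differ from the text elsewhere, so the 150 is weak evidence.
- **Effect on the design.** More patients raise power for the same 6-point target, and 5.0–5.2 points is still in the upper half of the 4–6 point range. This stands; a total of 400 does no harm to the inference.
- **Deliberate inflation.** Extra patients could have been meant to cover clustering by provider or the disease subgroups. The Sample Size section mentions neither; deaths and missing data are its only adjustments.

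**Conclusion.** The concern holds. The protocol's stated total of 400 is incompatible with both of its accrual plans and with its own completer count and power. Those four figures agree with one another at about 300. The gap is 96–100 patients, about 50 of them in the intervention arm.

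At 300–304, the stated loss leaves 112–122 completers per arm and about 85–87% power, as the plan says. At 400 it leaves 150–160 per arm and about 93–95%. These powers use the Sample Size section's simple two-sample comparison; they ignore the baseline adjustment and the provider random intercept described in the Data Analysis Plan.

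This is an inconsistency to reconcile, not a power shortfall. The visible documents do not show which total was intended.

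**What to change.** State one total and bring every dependent figure into line with it.

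**Option A, keep 400.**
- Restate accrual as 8 per site per month over the budgeted 25 months, or about 10.5 per site per month over 19 months.
- Remove the claim that 6 per site per month finishes on time.
- Change the completers to 150–160 per arm with about 93–95% power at d = 0.4, labelled as the simple two-sample calculation.
- Confirm or correct the 150 for the intervention database in Table 6.
- The average of one new intervention patient per site each week stands at 8 per month (8/2/4.35 = 0.92). At 10.5 per month it becomes 1.21 and needs changing.

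**Option B, restate the total as 300.**
- Change 400 to 300 in Study population and Sample Size, and 200 to 150 in the Aim 2a recruitment text.
- Recheck the ceiling of 120 patient interviews there, which would rise from 60% (120/200) to 80% (120/150) of the intervention arm.
- The accrual plans, 115 completers per arm and 85% power can then stand essentially as written.

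Option A needs only a wording amendment, but it gives up the slow-accrual fallback and uses the whole budgeted period at 8 per site per month. Option B also changes little text, but a smaller stated total needs re-approval; the stated power is not lost. Under either option, check Figure 2 against the chosen total.

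### The recruitment rates and durations in the protocol deliver about 300 randomized patients, not the stated 400

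*Protocol*

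**What the plan says.** Three places in the Protocol give the target. IV.B, Study population: "A total of 400 adult subjects will be randomized in a 1:1 ratio to one of 2 treatment arms". IV.C, Sample Size: "We plan to enroll 400 Veterans and anticipate 5% will die and 15-20% will have missing outcome data", followed by about 115 completers per arm and 85% power at an effect size of 0.4. IV.C, Recruitment Targets and Tracking, Aim 2a, refers to interviews with "at most 120 eligible patients of the 200 receiving the intervention will participate".

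The recruitment plan is under the same heading, Aim 1. The main plan reads "We will aim to randomize 8 patients per month at each site (16 total) over a 19 month period". For slower enrollment the protocol says "we will still be able to complete the study on time if 6 Veterans per month are randomized at each site", over 25 months. The Timeline text says the investigators "have budgeted for completing recruitment over 25 months" and that "The proposed study will be completed within a 4 year timeline". The timeline table marks start-up in Year 1 and recruitment in Years 2, 3 and 4. Section D and Table 5 schedule the last FACT-G at 12 months; section F puts the primary outcome at 6 months.

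Table 6 gives a sample size of 150 for the intervention database and 150 for the close-out summaries. The SAP states no sample size or accrual figure, so it does not settle the matter.

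**The concern.** A recruitment plan is a product of rate, sites and months, and that product should equal the sample size. Here it falls about 100 short under both plans. The stated rates are also the natural yardstick for the recruitment monitoring described in the Monitoring plan. Two sites that met the fallback rate every month would look on target, yet would reach the end of the budgeted window 25% below the stated size. Whether to stop near 300, extend recruitment or shorten follow-up would then be decided without a plan. A reader also cannot tell whether 400 or about 300 is the number on which the completer count and power rest.

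**Working it through.** **Inputs (Protocol).** Target 400; 2 sites; main plan 8 per site per month for 19 months; fallback 6 per site per month for 25 months; budgeted maximum 25 months; losses 5% deaths plus 15-20% missing; 115 completers per arm; two-sided alpha 0.05; effect size d = 0.4; timeline 48 months; last visit 12 months after enrollment.

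**1. The protocol's own power figure.** With the normal approximation, power = Φ(d√(n/2) − 1.96). At n = 115 per arm, 0.4 × √57.5 − 1.96 = 1.073, which gives 85.8%. The stated 85% reproduces, and Table 3 reproduces to within one patient per cell.

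**2. Accrual = rate per site × sites × months.**
- Main plan: 8 × 2 × 19 = 304, which is 96 short of 400.
- Fallback: 6 × 2 × 25 = 300, which is 100 short.
- Time to 400 at 12 a month: 400/12 = 33.3 months, against 25 budgeted.
- Rate needed for 400 in 25 months: 400/25 = 16 a month, or 8 per site.
- Rate needed for 400 in 19 months: 400/(19 × 2) = 10.5 per site per month.

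The main rate is unlikely to be a misprint. The protocol adds that it yields about one intervention patient per site per week, and half of 8 a month is 4.

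**3. Completers per arm = N × (1 − loss)/2, with loss 20-25%.**

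| Randomized | Completers per arm | Power at d = 0.4 |
|---|---|---|
| 300 | 112.5-120 | 85.1-87.3% |
| 304 | 114-121.6 | 85.5-87.7% |
| 400 | 150-160 | 93.4-94.7% |

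The stated 115 per arm (230 in all) implies a loss of 1 − 230/300 = 23.3% from 300, inside the stated range. From 400 it implies 1 − 230/400 = 42.5%, far outside it. Taking the losses in sequence instead of adding them changes little: 150 × 0.95 × 0.80 to 0.85 = 114-121 from 300, and 200 × 0.95 × 0.80 to 0.85 = 152-161.5 from 400.

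**4. Intervention records.** Half of 300 is 150, the Table 6 figure. Half of 400 is 200, the Aim 2a figure.

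**5. Calendar.** If recruitment starts after month 12 and lasts 25 months, the last patient is randomized at month 37, has the 6-month visit at month 43 and the 12-month visit at month 49. That is one month past 48, before any time for analysis. Those affected are the patients randomized in the last month: 12 of 300 at the fallback rate, or 16 of 400 at 16 a month (4% either way). A start by month 48 − 12 − 25 = 11 removes the overrun; a start after month 6 puts the last visit at month 43.

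**The case against.** The strongest reply is that nothing in the primary inference fails. Stopping near 300 leaves the 115 completers per arm and 85% power that the Sample Size section relies on. This is correct, and it limits the consequence. A reader might infer from the shortfall that the trial is underpowered; the protocol's own figures do not support that.

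A reader might also infer a long overrun: 400 patients at 12 a month would put the last 12-month visit at month 57.3 after a 12-month start-up, or 51.3 after six months. Those dates assume 33.3 months of recruitment, which the protocol does not plan; it budgets 25. Within that window the overrun is about one month. Even that depends on a table that shows only yearly columns here, although the text says it uses 6-month increments.

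Nor do the documents support a claim that 12-month utilization and mortality data would be lost. IV.A, item 14, provides for VA and non-VA record review, the VA Vital Status File and the National Death Index. The Timeline text and section D allow record collection for up to ten years. What cannot be recovered from records is the 12-month FACT-G and what patients themselves would report at that visit.

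Finally, Figure 2, which carries the accrual goals, is not available here. It might state a different target, but it cannot change the product of rate and months. The mismatch with 400 stands.

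**Conclusion.** The accrual figures contradict the sample size. Both plans give 300-304, which is 96-100 patients (24-25%) below 400, and the assurance about the fallback rate is false for 400. This is plain arithmetic on stated figures. The completer count and two rows of Table 6 also fit about 300, so correcting the recruitment paragraph alone would leave the protocol inconsistent. One explanation is a target of about 300 raised to 400 without updating the rest; that is an inference, since the documents do not give the history. The matter should be corrected, but it does not threaten the 6-month primary comparison: power is about 85-87% at 300 and 93-95% at 400, assuming the stated losses and d = 0.4.

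The timeline point is secondary and conditional. If start-up fills Year 1, the last 12-month visits run to month 49, and any patient randomized in Year 4 has that visit after Year 4. Within the 25-month window the 6-month visits are all done by month 43.

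**What to change.** State one sample size and bring Study population, Timeline, Recruitment Targets and Tracking (Aims 1 and 2a), Sample Size and Table 6 into line with it. There are two coherent versions:

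- **Keep 400.** Give 16 a month for 25 months as the required rate, restate completers as about 150-160 per arm with about 93-95% power at d = 0.4, and change the 150s for the intervention database and close-out summaries in Table 6 to 200. The cost is that the present main rate would then be needed for the whole budgeted window, so no slower fallback remains.
- **State about 300.** The two accrual plans, 115 completers per arm, about 85% power and the 150s can stay. The 400 in Study population and Sample Size, and the 200 under Aim 2a, change. The cost is a smaller declared trial.

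In either case, state an end of follow-up that covers last randomization plus 12 months, or say that the 12-month FACT-G survey will be administratively incomplete for the last patients enrolled. These are edits to protocol figures; the design and the 6-month primary analysis do not change.

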#### **Aim 2a:**

**Patient interviews:** We anticipate at most 120 eligible patients of the 200 receiving the intervention will participate, as they have already participated in the intervention and would be likely to offer feedback.

**Intervention personnel:** We expect all intervention team members to participate as they are invested in the intervention and would be likely to want to provide feedback.

[figure not shown]
**Primary care providers whose patients have received the intervention:** We expect approximately 100 providers will participate.

### Recruitment Process

#### **Aim 1:**

1. We are requesting a HIPAA waiver to allow us to screen administrative databases and review medical records of Veterans seen at each study site to identify Veterans who may be appropriate for the study. Data sources for screening include CDW Production, CDW Raw, CAN Score, PACT Implementation Index, Real SSN, Scrambled SSN, CAPRI, and VSSC web reporting.
2. Administrative data will be pulled according to the inclusion/exclusion criteria outlined in section "Study population." We will also use a research database of veterans who consented to be contacted for future research studies as part of the VA CASA trial (COMIRB #11-0969) and meet eligibility requirements. Providers within the VA system can also choose to tell potential study participants about the study and provide them with a flyer for the patient to write in patient contact information and either return to study staff or call study staff directly for more information about the study.
3. Study staff will review medical records to confirm eligibility criteria.
4. Veterans who meet initial eligibility screening will be mailed a letter that describes the study and gives them the opportunity to call the recruitment team if they are interested or decline by returning a postage paid letter and envelope. The letter will also say that the Veteran will be contacted by phone if the study team does not receive communication from the Veteran. Veterans can also opt out during the phone call.
5. Interested Veterans will be asked to verbally consent to further phone screening to verify eligibility (see included script).

